### 59 Percentage below 54 mg/dl (non-inferiority):

60

- 61 *Null Hypothesis:* The difference in mean CGM-measured % below 54 mg/dl between the 6  
62 weeks follow-up and baseline is greater than or equal to +1%.
- 63 *Alternative Hypothesis:* The difference in mean CGM-measured % below 54 mg/dl between the  
64 weeks follow-up and baseline is less than +1%.

65

### 66 Percentage above 180 mg/dl (superiority):

67

- 68 *Null Hypothesis:* There is no difference in mean CGM-measured % above 180 mg/dL between  
69 the 6 weeks of follow-up and baseline.
- 70 *Alternative Hypothesis:* The mean CGM-measured % above 180 mg/dL is different at baseline  
71 than the mean over 6 weeks of follow-up.

72

## 73 3. Sample Size

74 The planned cohort of  $N=30$  participants, with the goal of at least  $N=24$  completing the study, is a  
75 convenience sample not based on statistical principles.

76

## 77 4. Outcome Measures

78

### 79 4.1. Primary Efficacy Endpoint:

80

- 81 Non-inferiority in CGM-measured % below 54 mg/dl between the 6 weeks follow-up. This is the  
82 only non-inferiority and one-sided outcome in the study.
- 83 Superiority in CGM-measured % above 180 mg/dl between the 6 weeks follow-up.

84

### 85 4.2. Secondary Efficacy Endpoints

86

- 87 CGM overall metrics during follow-up:
  - 88 % in range 70-180 mg/dL
  - 89 % in tight glycemic range 70-140 mg/dL
  - 90 mean glucose
  - 91 glucose variability measured with the coefficient of variation
  - 92 % <70 mg/dL
  - 93 % <54 mg/dL (superiority)

- % >250 mg/dL
- % >300 mg/dL
- CGM metrics by time of day:
  - Calculate all CGM metrics listed above (including the two primary outcomes) for:
    - All 24 hours of the day (the two primary outcomes are over 24hr)
    - Daytime only (06:00AM to 00:00AM)
    - Nighttime only (00:00AM to 06:00AM)
    - During and after the scheduled exercise sessions
- Up to 4hr post-prandial CGM metrics:
  - Area Under the Curve (AUC)
  - Maximum
- Insulin over follow-up:
  - Total daily insulin (units and units/kg)
  - Total daily bolus (units and units/kg)
  - Total daily basal (units and units/kg)
- Weight and body mass index at 6 weeks
- Questionnaires:
  - Administered at enrollment only
    - Tandem Study-Specific Survey – 4 items.
    - Altarum Consumer Engagement Measure – 6 items and total score.
  - Administered at the start of open-loop and again at the start of the closed loop
    - Tandem Pump Training Survey – 4 items.
  - Administered at enrollment, start of closed-loop period, and 6 weeks
    - DAWN Impact of Diabetes Profile – 7 items and total score.
    - Diabetes Impact and Device Satisfaction Scale – 12 items and two subscale scores (device satisfaction and diabetes impact).
    - PROMIS Sleep-Related Impairment Questionnaire – 8 items and total score.
  - Administered at the start of closed-loop period and at 6 weeks
    - System Usability Scale – 10 items and total score.

#### 4.3 Calculation of Overall CGM Metrics (primary and secondary):

- One Week of Baseline: The last 7 days of personal CGM data before enrollment or last 7 days of CGM run-in data will serve as baseline. If a participant has <24hr of data in the last 7 days of CGM personal or run-in and if more CGM data are available beyond the 7 days, then will go backwards 24hr at one time until the minimum of 24hr of CGM data are reached. At least 24hr of data during baseline are required for the glycemic metrics to be calculated. These are Dexcom sensor data.
- Six Weeks of CLC use: All CGM data following the midnight of the initiation of CLC use visit day and the midnight right before the end of study visit day will be included irrespective if the system was in closed-loop mode or not. Since the exercise sessions are designed as challenges to the system and the data to be analyzed for safety events, the CGM data between the start of the exercise and 6:00AM next morning will be analyzed separately (see Section 8.1 below) and not included here. On the other hand, since the meals are not designed to be challenges to the system, the CGM data following the meals will be included here even if also analyzed separately (see

Section 8.1 below). If the end of 6 weeks of CLC use visit is more than 6 weeks away from the CLC use initiation visit for a participant, then the CGM data will be truncated at 6 weeks (i.e., 42 days). At least 168hr of data during these 6 weeks of CLC use are required for the glycemic metrics to be calculated and for a participant to be included in the primary and secondary analyses. These are Tandem pump CGM data and will include data following meals and during exercise periods.

- Two-four Weeks of Open Loop (OL) use: All CGM data between the initiation of Open-Loop use and the start of CLC will be used. At least 24hr of data during this period are required for the glycemic metrics to be calculated. These are Tandem pump CGM data.
- All CGM metrics during baseline, OL, and CLC periods will be calculated giving equal weight to each sensor reading for each participant.

#### 4.4 Calculation of Post-Prandial CGM Metrics

- This analysis will be limited to participants using meal boluses.
- Meal boluses will be identified by a carb announcement >15g in the pump log.
- Will be calculated only during the 6 weeks of CLC use and are based on the Tandem pump CGM data.
- In case a participant switches between basal-only and basal plus boluses; only meals during bolus use can be identified and included in these analyses.
- Will include all CGM data between the carb announcement and the earlier of 4hr from the end of the meal or the beginning of the next meal bolus or exercise session.
- At least 30min (or 6 CGM readings) are required for each individual meal for the CGM metrics to be calculated.
- Each CGM reading following a particular meal will be given equal weight.
- The unit of analysis is an individual meal and any participant with at least one meal will be included in these analyses.

#### 4.5 Calculation of CGM Metrics during Scheduled Exercise Sessions and the Following Night

- Will be calculated only during the 6 weeks of CLC use and are based on the Tandem pump CGM data.
- Will be calculated only if the exercise session was recorded on CRF.
- All data between the start of the exercise challenge and 6:00AM next morning will be included.
- For each exercise, two different periods will be considered, and two separate glycemic metrics will be calculated:
  - During and two hours following the end of the exercise – the period between the start and 2 hours following the end of exercise as recorded on CRF, and
  - Overnight following the exercise – the period between 2 hours following the end of the exercise and 6:00AM next morning.
- At least 30min (or 6 CGM readings) are required for each one of the two periods associated with an individual exercise session for the CGM metrics to be calculated.
- Each CGM reading during an exercise session will be given equal weight.
- The unit of analysis is an individual exercise session and any participant with at least one exercise challenge completed will be included in these analyses.

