#### 517 **4.1.3 Home Use of the Study System**

518 After training on closed-loop aspects of the study system has been completed, participants will  
519 proceed with home use (meaning free-living use at school, home, etc.) of the study pump.  
520 Participants will be asked to complete an exercise log, and use the exercise activity mode of the  
521 study pump at least once per week for a minimum of 30 minutes of exercise.

522 Follow up visits will occur per the visit listing described below. If necessary, visits should be  
523 completed out-of-window rather than missed. A visit is not considered missed until the next  
524 visit/phone window opens.

525 The goal will be for all participants to complete all scheduled visits. However, participants who  
526 (because of unforeseen circumstances or due to changes in contact precautions that may be  
527 needed during the evolving COVID-19 pandemic) are unable or unwilling to return for all  
528 follow-up visits will be permitted to return for key visits only as an alternative to withdrawal  
529 from the study. When a participant is placed into this status, missed visits will not be recorded as  
530 protocol deviations (since they would not be recorded as protocol deviations if the participant  
531 was dropped from the study).

532 Additional office visits may occur as needed.

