#### 533 **Study Specific Guidance for the Exercise Challenges**

534 Study staff will review with participants that for each weekly exercise challenge, they will be  
535 required to:

- 536 1. Have extra carbohydrate containing snacks on hand during and after exercise.
- 537 2. Consider activation of exercise activity up to 45 minutes ahead of actual exercise, to allow  
538 for less insulin on board when starting exercise.
- 539 3. Consider reducing the last meal bolus prior to exercise as a way to reduce insulin on board  
540 and limit hypoglycemia.

541 4. Participants will write down the type of exercise performed, as well as the start and stop time  
542 of each exercise session on the study logbook, as this may not correlate exactly with exercise  
543 activity use on the pump.

544 5. Participants will be instructed that they may stop the exercise challenges at any point for  
545 injury or development of new symptoms (development of chest pain/pressure, feeling unwell,  
546 development of hypoglycemic symptoms, undue shortness of breath, signs of poor perfusion  
547 (leg pain/claudication), or for any other reason.

548 6. Participants will then notify the site within 24 hours after completion of each exercise  
549 challenge. The site staff will review for adverse events or new symptoms (See section 4.1.11)  
550 and review guidance on the need to stop future exercise challenges if any adverse events or  
551 new symptoms occurred per clinician judgement based on the severity of symptoms.

552 7. If a participant does not call within a week, study staff should perform an unscheduled  
553 contact to remind the participant of the required follow-up and encourage completion of the  
554 remaining exercise challenges. If a participant has to reschedule their exercise sessions, or  
555 postpone them for any reason (for example, the gym where they walk on a treadmill is too  
556 crowded and they did not want to enter to limit exposures due to COVID-19), they will be  
557 allowed to do so, and this will not be considered a protocol deviation. Similarly, if future  
558 exercise challenges are cancelled due to safety concerns, this will not be considered a  
559 protocol deviation.

560 Each clinical site can customize this guidance per their established clinical practice, to include  
561 how long to keep exercise activity active after the exercise challenge has ended.

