#### Calculation of CGM metrics

1191       • Baseline values will be taken from the last 7 days of the run-in, or for participants who  
1192       can skip the run-in baseline values will be taken from their personal CGM during the 7  
1193       days prior to initiating CLC. At least 24hr of data during this baseline period are required  
1194       for the glycemic metrics to be calculated.  
1195       • Follow-up values will be calculated using CGM data from the 6-week period of CLC use.  
1196       These will be limited to participants who have at least 168 hours of CGM data available  
1197       during the 6-week CLC use period.  
1198       • Exploratory analyses will include all CGM data between the initiation of Open-Loop use  
1199       and the start of CLC will be used. At least 24hr of data during this period are required for  
1200       the glycemic metrics to be calculated.  
1201       • Separate values for each CGM metric (except for post-prandial peak and 4-hour AUC)  
1202       will be calculated for:  
1203           ➤ Overall: 24 hours of the day  
1204           ➤ Daytime: CGM readings from 6:00 am – 11:59 pm  
1205           ➤ Nighttime: CGM readings from midnight – 5:59 am  
1206           ➤ During logged exercise challenges

1207

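### The overnight-after-exercise window in SAP 4.5 has no clock-time start, so for sessions ending before 16:00 more than half of it is daytime by the SAP's own definition

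*SAP*

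**What the plan says.** SAP 4.5 is headed "Calculation of CGM Metrics during Scheduled Exercise Sessions and the Following Night". It takes all CGM data from the start of a challenge to 06:00 the next day and divides them in two. The first period runs from the start of exercise to 2 hours after its end. The second, labelled as overnight, is "the period between 2 hours following the end of the exercise and 6:00AM next morning". Within a session every CGM reading has equal weight, the session is the unit of analysis, and each period needs 30 minutes of data (6 readings) to yield a value.

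Night is defined elsewhere. SAP 4.2 has "Nighttime only (00:00AM to 06:00AM") and, for the remainder, "Daytime only (06:00AM to 00:00AM"). Protocol 9.4.2 agrees: "Nighttime: CGM readings from midnight – 5:59 am".

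On timing, Protocol 4.1.3 asks for use of the exercise mode of the "study pump at least once per week for a minimum of 30 minutes of exercise". It sets frequency and duration but no time of day, and sessions may be rescheduled. The clock times are known: "Participants will write down the type of exercise performed, as well as the start and stop time".

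SAP 4.3 gives the reason for separate handling: "Since the exercise sessions are designed as challenges to the system and the data to be analyzed for safety events". Protocol 9.7 makes the exercise metrics descriptive, within closed-loop use only.

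**The concern.** A reader who sees an overnight glucose metric after exercise will take it to describe the night. As defined, it describes whatever lies between 2 hours after exercise and 06:00. After a morning session that includes late morning, afternoon and evening, with their meals. SAP 4.4 cuts its post-meal windows at the next meal bolus or exercise session; SAP 4.5 has no such limit.

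At stake is the readability of a safety summary. The study is meant to assess safety and to supply data for designing a larger trial. If the post-exercise night is tabulated from windows of very different length and content, the figures cannot be compared across sessions, set beside the general nighttime metric, or carried forward as what happens at night after exercise.

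**Working it through.** The plan gives no figure for this window, so there is nothing of its own to reproduce. Clock arithmetic is enough.

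**Inputs**
- Window: exercise end + 2 h to 06:00 next day (SAP 4.5).
- Night: 00:00 to 06:00, 6 h (SAP 4.2, Protocol 9.4.2).
- Weighting: equal per reading, so each part of the window counts in proportion to its length (SAP 4.5, assuming complete data).
- Time of day of exercise: unrestricted (Protocol 4.1.3).

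**Window length and night share**

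Let exercise end at hour T on the 24-hour clock, T ≤ 22. Taking 06:00 next day as hour 30:

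window length = 30 − (T + 2) = 28 − T hours; night share = 6/(28 − T).

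| Exercise ends | Window (h) | Night share |
|---|---|---|
| 08:00 | 20 | 6/20 = 30.0% |
| 10:00 | 18 | 6/18 = 33.3% |
| 12:00 | 16 | 6/16 = 37.5% |
| 14:00 | 14 | 6/14 = 42.9% |
| 16:00 | 12 | 6/12 = 50.0% |
| 18:00 | 10 | 6/10 = 60.0% |
| 20:00 | 8 | 6/8 = 75.0% |
| 22:00 | 6 | 6/6 = 100% |

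The share equals one half when 28 − T = 12, that is T = 16:00. Earlier sessions give a mostly daytime window; later ones do not.

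**How many sessions this could touch (assumption)**

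The documents give no distribution of exercise times. If end times were uniform from 08:00 to 20:00, the fraction ending before 16:00 would be 8/12 = 67%. The mean window would be 28 − 14 = 14 h, so night would be 6/14 = 43% of the pooled readings. If night were instead taken as 22:00 to 06:00 (not the SAP's definition), the share for sessions ending by 20:00 would be 8/(28 − T), with break-even at 12:00.

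**Comparability**

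Take the same night in two participants, each with one 30-minute episode below 54 mg/dL and, for illustration, no other lows. Over the 6 h night it is 0.5/6 = 8.3%. In the SAP 4.5 window it is 0.5/20 = 2.5% after an 08:00 end and 0.5/10 = 5.0% after an 18:00 end. The nights are identical; the reported values differ by a factor of two.

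**Direction of any effect**

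Window value = share × night rate + (1 − share) × day rate. With a 12:00 end (share 0.375) and assumed rates below 54 mg/dL:

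| Night rate | Day rate | Window value | Against night rate |
|---|---|---|---|
| 2.0% | 0.2% | 0.750 + 0.125 = 0.88% | lower |
| 1.0% | 0.2% | 0.375 + 0.125 = 0.50% | lower |
| 0.5% | 0.5% | 0.50% | same |
| 0.2% | 1.0% | 0.075 + 0.625 = 0.70% | higher |

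The sign depends on rates that the documents do not give.

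**Minimum data**

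Six readings per 30 minutes is 12 per hour. After an 08:00 end the window holds 20 × 12 = 240 possible readings, of which 14 × 12 = 168 precede midnight. Any 6 of those 168 satisfy the rule.

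**The case against.** The strongest reply is that the two periods divide the interval from exercise start to 06:00 without gap or overlap, and that this is the interval SAP 4.3 sets aside. Low glucose in the afternoon or evening after a morning session is also a post-exercise safety signal, and the window captures it. No data are lost, and a plainer label would remove much of the problem. This stands, and it is why the repair should keep every reading.

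Three stronger readings are tempting and are not supported:
- A reader might infer that the window is mostly daytime after any daytime exercise. By the SAP's own day (06:00 to midnight), sessions ending from 16:00 to 22:00 are daytime sessions, yet their windows are 50% to 100% night.
- A reader might infer that nocturnal hypoglycemia is diluted or understated. That requires fewer lows by day than at night, which the documents do not establish.
- A reader might infer that the metric exists to show nocturnal hypoglycemia. The section title points towards the night, but the stated purpose is safety events in general.

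The practical weight is also limited. The metrics are descriptive, severe hypoglycemia is tabulated separately (SAP 8), and each challenge prompts an adverse-event contact within 24 hours (Protocol 4.1.11). An overnight value with no night reading needs near-total sensor loss at night, in participants who had to show at least 85% CGM capture beforehand.

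Finally, SAP 7.1 was not available in the text reviewed, so a further split by time of day there cannot be ruled out. In the available text, time-of-day and exercise metrics are listed separately and not crossed. SAP 4.3 says both that exercise-to-06:00 data are left out of the overall metrics and that exercise-period data are in them, so it is unclear whether the general nighttime metric covers these nights.

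**Conclusion.** The point holds as one of definition and comparability. The overnight label does not match the documents' own night, and the night share runs from 30% for an 08:00 end to 100% for a 22:00 end. For sessions ending before 16:00 more than half the window is daytime. This rests only on the SAP's definitions, equal weighting and complete data within the window. How many sessions are affected is unknown; the 67% above is an assumption about exercise times. The bias in time below 54 or 70 mg/dL has no determinable direction, so the plan should not be described as hiding nocturnal lows. The effectiveness criterion and both primary tests are untouched by this choice of split. The change is worth making because it alters the reported post-exercise night figures at trivial cost.

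**What to change.** In SAP 4.5:
- Define the overnight period as running from the later of midnight following the session and exercise end + 2 h, until 06:00. Taking the later of the two matters for sessions ending after 22:00. After a 23:00 end the first period runs to 01:00, and a fixed midnight start would count that hour twice.
- Apply the 30-minute (6-reading) minimum to readings inside that period.
- Report exercise end + 2 h to midnight, where it exists, as a separate third period with its own minimum.

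For any session ending by 22:00 the overnight period is then 6 h and wholly night, and all data from exercise start to 06:00 are still used. Start and stop times are already recorded, so the cost is SAP wording, a changed time filter and one extra period to tabulate. A comparison with nights not preceded by exercise could be added but is optional and not part of this repair.

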## 4.6 Calculation of Insulin Metrics

184     • Will include only days with complete insulin data and at least 7 such days are required for the  
185       metrics to be calculated. If there are not such 7 days, the participants will not be included in the  
186       insulin analyses. Since Tandem pump automatically generates a basal record every hour, at least  
187       20 such hourly records are required for a day to be considered complete with insulin data and to  
188       be counted towards the minimum of 7 days.  
189     • Will be calculated only during the 6 weeks of CLC use and are based on the Tandem pump  
190       insulin delivery data.  
191     • As with the CGM metrics, if a participant stayed in the study more than 6 weeks, then the insulin  
192       data will be truncated at 6 weeks from the initiation of CLC use.  
193     • Weight at baseline will be used to calculate units/kg metrics.

194  
195  
196 **4.7. Questionnaires**

197 Participants are allowed to skip specific questionnaires or items within a questionnaire. The data might  
198 therefore include some missing items. If applicable, questionnaires will be scored according to the  
199 instructions given in the manual. If a total or a sub-scale score is calculated but no instructions exist,  
200 then at least 75% of the items should be non-missing for the total or sub-scale score to be calculated.

201  
202 **4.8 Analysis Windows**

203 Analysis windows apply to the following outcomes measured at 6-week final visit:

204     • Weight  
205     • Questionnaires

206 To be included in the corresponding analyses, these data must be collected between days 28 and 56 from  
207 the beginning of CLC period. The target date is 42 days from the beginning of CLC period.

208 This does not apply to the CGM and insulin metrics which are calculated as described above.

211  
212 **5. Description of Statistical Methods**

213     **5.1. General Approach:**

214     • Since this is not a randomized trial, the intention-to-treat (ITT) principle does not apply.  
215     • In the unlikely event that an enrolled participant is later found to be ineligible, the participant  
216       will be excluded from all analyses.  
217     • Otherwise, all enrolled participants with at least 168h of CGM data during the 6-week of CLC  
218       use will be included in the primary and secondary analyses.  
219     • The primary and secondary CGM analyses will include the baseline and the 6-week of CLC use  
220       periods. All p-values that will be calculated refer to these paired baseline-CLC differences.  
221     • All p-values, apart from the primary CGM-measured % below 54 mg/dL, will be two-sided.  
222     • Only CGM metrics, weight/BMI, and some questionnaires are measured both at baseline and  
223       follow-up. As such, p-values will be calculated only for CGM and weight/BMI metrics.  
224     • Standard diagnostics, based on the paired differences between the CLC and baseline periods, will  
225       be performed for all analyses. If the paired differences do not follow an approximate normal  
226       distribution, non-parametric methods will be used.  
227

228 distribution, then a non-parametric comparison based on ranks will be performed. Previous  
229 experience suggests that no nonparametric analyses will be necessary for % time in range 70-180  
230 mg/dL, % above 180 mg/dL, or mean glucose. Other outcomes like % below 54 mg/dL are  
231 skewed; however, the differences between the two periods may follow a normal distribution and  
232 there may be no need for nonparametric analyses.

233 • Exploratory CGM analyses will include all three periods: baseline, OL, and CLC use. No p-  
234 values will be calculated for these exploratory analyses; but only summary statistics like mean  
235 (SD) or median (IQR) and plots.

236

